**Note: The Type of Submission cannot be changed after this application has been submitted for review.**

4 Original Version #:  
25MAR2022

ID: VIEW4DF8709A33C00  
Name: v2\_Introduction Page

## Resources

If this study is a collaborative UM/VA study, please clarify which resources are being used at each institution.

1 \* **Describe the time that the Principal Investigator will devote to conducting and completing the research:**

The principal investigator will devote 20% effort (equivalent to 8 hours per week) to this project for the duration of the study to conduct and complete the research.

2 \* **Describe the facilities where research procedures are conducted:**

This study will be conducted out of University of Maryland School of Nursing (SON) and recruitment will occur mainly from University of Maryland Greenebaum Comprehensive Cancer Center (UMGCC) in Baltimore, MD. [name] has sufficient office space, computers, locked cabinets, and other resources to conduct this study. [name] has access to a dedicated clinical testing room on the 7th floor of the School of Nursing to conduct consents and perform study activities.

3 \* **Describe the availability of medical and/or psychological resources that subjects might need as a result of anticipated consequences of the human research:**

We do not anticipate the need for additional medical or psychological resources as a result of participation in this study. However, in case the need arises, participants will have access to all of the medical and/or psychological resources available at the University of Maryland Greenebaum Comprehensive Cancer Center (UMGCC) and the University of Maryland Medical Center (UMMC) more broadly. Any participants who experience emotional distress while completing study procedures will be referred to their healthcare provider. In the case of a medical or psychiatric emergency (e.g., verbalization of suicidal thoughts), we will call 911 and ensure safe transport of the participant to a hospital.

4 \* **Describe the process to ensure that all persons assisting with the research are adequately informed about the protocol, the research procedures, and their duties and functions:**

[name] will oversee all training of the study team members to ensure proper execution of the research procedures. All members of the study team will have working knowledge of the protocol and expert knowledge in the areas in which they are directly involved. [name] will meet with the study coordinator(s) at least biweekly and more frequently as needed to discuss the progress and logistics of the study. [name] will meet with the other members of the study team at a frequency that is decided upon initiation of their involvement, based on their individual role.

ID: V1EW4DF83CB976400

Name: v2\_Resources

## Funding Information

1 \* Indicate who is funding the study:

- Federal**
- Industry
- Department / Division / Internal**
- Foundation
- Private
- State Agency

2 \* What portion of the research is being funded? (Choose all that apply)

- Drug
- Device
- Staff**
- Participant Compensation**
- Procedures**
- Other**

3 Please discuss any additional information regarding funding below:

This study is being supported by the Institute of Clinical and Translational Research (ICTR) Accelerated Translational Incubator Pilot (ATIP) grant, funded by the National Center for Advancing Translational Science (NCATS), and start-up funds to [name].

ID: VIEW4DF85DF452400  
Name: v2\_Funding Information

## Research Protocol

1 \* Do you have a research protocol to upload?

Yes

No, I do not have a research protocol and will use the CICERO application to enter my study information

2 If Yes, upload the research protocol:

Name	Created	Modified Date
------	---------	---------------

There are no items to display

ID: VIEW4E00563F8D000  
Name: v2\_Research Protocol

**Risk Level**

**What is the risk level of your study? (Ultimately, the IRB will determine the appropriate risk level and your designation is subject to change.)**

\* Choose One:

Minimal - The probability & magnitude of harm/discomfort anticipated in the research are not greater in and of themselves than those ordinarily encountered in daily life or during the performance of routine physical or psychological examinations/tests.

Greater Than Minimal - Does not meet the definition of Minimal Risk.

ID: VIEW4E02805225800  
Name: v2\_Risk Level

## Exempt Categories

You indicated on the "Risk Level" page that this study is Minimal Risk.

1 \* Please review the following categories to determine if your research may be Exempt from IRB oversight. If you believe that your study qualifies as Exempt, select the Category under which it qualifies. If your research does not qualify as Exempt, select "**The research does not qualify as Exempt**".

**Category 1:** Research, conducted in established or commonly accepted educational settings that specifically involves normal educational practices that are not likely to adversely impact students' opportunity to learn required educational content or the assessment of educators who provide instruction. This includes most research on regular and special education instructional strategies, and research on the effectiveness of or the comparison among instructional techniques, curricula, or classroom management methods.

**Category 2:** Research that only includes interactions involving educational tests (cognitive, diagnostic, aptitude, achievement), survey procedures, interview procedures, or observation of public behavior (including visual or auditory recording) if at least one of the following criteria is met:

- i. The information obtained is recorded by the investigator in such a manner that the identity of the human subjects cannot readily be ascertained, directly or through identifiers linked to the subjects.
- ii. Any disclosure of the human subjects' responses outside the research would not reasonably place the subjects at risk of criminal or civil liability or be damaging to the subjects' financial standing, employability, educational advancement, or reputation.
- iii. The information obtained is recorded by the investigator in such a manner that the identity of the human subjects can readily be ascertained, directly or through identifiers linked to the subjects, and an IRB conducts a limited IRB review to make the determination required by .111(a)(7).

**Category 3:** Research involving benign behavioral interventions (brief in duration, harmless, painless, not physically invasive, not likely to have a significant adverse lasting impact on the subjects, and not offensive or embarrassing) in conjunction with the collection of information from an adult subject through verbal or written responses (including data entry) or audiovisual recording if the subject prospectively agrees to the intervention and information collection and at least one of the following criteria is met:

- i. The information obtained is recorded by the investigator in such a manner that the identity of the human subjects cannot readily be ascertained, directly or through identifiers linked to the subjects.
- ii. Any disclosure of the human subjects' responses outside the research would not reasonably place the subjects at risk of criminal or civil liability or be damaging to the subjects' financial standing, employability, educational advancement, or reputation.
- iii. The information obtained is recorded by the investigator in such a manner that the identity of the human subjects can readily be ascertained, directly or through identifiers linked to the subjects, and an IRB conducts a limited IRB review to make the determination required by .111(a)(7).

**Category 4:** Secondary research for which consent is not required: Secondary research uses of identifiable private information or identifiable biospecimens, if at least one of the following criteria is met:

- i. The identifiable private information or identifiable biospecimens are publicly available.
- ii. Information, which may include information about biospecimens, is recorded by the investigator in such a manner that the identity of the human subjects cannot readily be ascertained directly or through identifiers linked to the subjects, the investigator does not contact the subjects, and the investigator will not re-identify subjects.
- iii. The research involves only information collection and analysis involving the investigator's use of identifiable health information when that use is regulated under 45 CFR parts 160 and 164, subparts A and E [HIPAA], for the purposes of "health care operations" or "research" as those terms are defined at 45 CFR 164.501 or for "public health activities and purposes" as described under 45 CFR 164.512(b).
- iv. The research is conducted by, or on behalf of, a Federal department or agency using government-generated or government-collected information obtained for nonresearch activities, if the research generates identifiable private information that is or will be maintained on information technology that is subject to and in compliance with section 208(b) of the E-Government Act of 2002, 44 U.S.C. 3501 note, if all of the identifiable private information collected, used, or generated as part of the activity will be maintained in systems of records subject to the Privacy Act of 1974, 5 U.S.C. 552a, and, if applicable, the information used in the research was collected subject to the Paperwork Reduction Act of 1995, 44 U.S.C. 3501 et seq.

**Category 5:** Research and demonstration projects that are conducted or supported by a Federal department or agency, or otherwise subject to the approval of department or agency heads (or the approval of the heads of bureaus or other subordinate agencies that have been delegated authority to conduct the research and demonstration projects), and that are designed to study, evaluate, improve, or otherwise examine public benefit or service programs, including procedures for obtaining benefits or services under those programs, possible changes in or alternatives to those programs or procedures, or possible changes in methods or levels of payment for benefits or services under those programs. Such projects include, but are not limited to, internal studies by Federal employees, and studies under contracts or consulting arrangements, cooperative agreements, or grants. Exempt projects also include waivers of otherwise mandatory requirements using authorities such as sections 1115 and 1115A of the Social Security Act, as amended.

**Category 6:** Taste and food quality evaluation and consumer acceptance studies:

- i. If wholesome foods without additives are consumed, or
- ii. If a food is consumed that contains a food ingredient at or below the level and for a use found to be safe, or agricultural chemical or environmental contaminant at or below the level found to be safe, by the FDA or approved by the EPA or the Food Safety and Inspection Service of the U.S.D.A.

- The research does not qualify as Exempt.

**Type of Research**

1 \* Indicate **ALL** of the types of research procedures involved in this study (Choose all that apply):

- Use of unapproved drug(s)/biologic(s) or approved drug(s)/biologic(s) whose use is specified in the protocol.
- Evaluation of food(s) or dietary supplement(s) to diagnose, cure, treat, or mitigate a disease or condition.
- Use of device(s) whose use is specified in the protocol
- Psychological/Behavioral/Educational Method or Procedure (i.e., survey, questionnaires, interviews, focus groups, educational tests).
- Sample (Specimen) Collection and/or Analysis (including genetic analysis).
- Data Collection or Record Review (i.e., chart review, datasets, secondary data analysis).
- None of the above.

2 \* Is this study a clinical trial OR will this study be registered at ClinicalTrials.gov?

A clinical trial is a research study in which one or more human subjects are prospectively assigned to one or more interventions (which may include placebo or other control) to evaluate the effects of those interventions on health-related biomedical or behavioral outcomes.

Yes  No

ID: VIEWHE0280569E000  
Name: V2\_Type of Research

## Lay Summary

1 \* Provide a summary of the background and purpose of the study in language that can be understood by a person without a medical degree.

Cancer-related fatigue affects at least 30-90% of patients with cancer, depending on the type of cancer and their treatment(s) (e.g., chemotherapy, radiation). It is not relieved by sleep or rest, and it sometimes can persist for years after a person's cancer was treated. The fatigue can be so bad that people cannot return to work, hobbies, family roles, or other daily activities, thereby greatly reducing quality of life. The causes of this fatigue are unknown, and we currently do not have anything that can reliably prevent or cure the fatigue. However, there are recent data suggesting that circadian rhythm, or a person's internal body clock, may be disrupted by the cancer experience and contribute to fatigue. Food intake is an external cue that can entrain circadian rhythm. We recently showed that cancer survivors are willing and able to eat all their food within a 10-hour eating window—a practice called time-restricted eating. Herein, we are testing time-restricted eating against a control group to see if time-restricted eating can indeed alleviate cancer-related fatigue.

All participants will be asked to use the myCircadianClock smartphone app to log their food intake and weekly body weight measurements. The app can also be used to log sleep (recommended), exercise (optional), and other health measures (optional). The participants assigned to the time-restricted eating group will be asked to eat all their food in a 10-hour window during the day. People can choose their start time based on their schedule and preferences, but we ask that the window is the same for the whole study (e.g., 7am-5pm, 9:30am-7:30pm). Black coffee and unsweetened tea are allowed before the eating window, and water and medicines are allowed at all times. The participants in the control group will not be restricted to when they can eat. Participants in both groups will give us valuable information regarding how daily behaviors (e.g., diet, physical activity, sleep patterns) are related to the experience of fatigue.

The first aim of our project is to test whether we are able to deliver a 12-week time-restricted eating program. The second aim is see if participants in the time-restricted eating group have less fatigue at week 12 compared to those in the control group, taking into account their fatigue at the beginning of the study. To look more closely at the biology and physiology underlying fatigue, we will measure circadian rhythm at the beginning, the middle (week 6), and the end of the study (week 12) using a wrist-worn actigraph (like a Fitbit or Apple Watch), as well as sugar metabolism using a continuous glucose monitor (nonintrusive device that sticks to the back of the upper arm). We hypothesize that time-restricted eating will lead to less fatigue, a stronger circadian rhythm, and healthier sugar metabolism.

ID: VIEW4E92805CF7000  
Name: v2\_Lay Summary

## Justification, Objective, & Research Design

If you uploaded a separate research protocol document in the 'Research Protocol' page, cite the applicable section and page numbers from that document in the answer boxes below.

1 \* Describe the purpose, specific aims, or objectives of this research. State the hypothesis to be tested:

This pilot randomized controlled trial will test the effects of time-restricted eating vs. an unrestricted eating pattern (i.e., control) on persistent cancer-related fatigue, circadian rhythm, and metabolism. These data build upon a study conducted by [name] (PI) that established the feasibility and safety of time-restricted eating among cancer survivors—cancer survivors were willing and able to eat within a 10-hour window for 14 days. The specific aims are as follows:

Aim 1: To assess the feasibility of time-restricted eating for 12 weeks, utilization of the myCircadianClock app, continuous interstitial glucose monitoring, and the wrist-worn actigraph. We hypothesize that 80% of participants will provide evaluable data regarding their eating window via the app at baseline and 12 weeks. We also hypothesize that at least 80% of participants who are in the time-restricted eating arm and provide evaluable data will eat within a daily average window that is  $\leq 10$  hours.

Aim 2: To estimate the preliminary efficacy of a 12-week time-restricted eating intervention vs. an unrestricted eating pattern on patient-reported fatigue among fatigued cancer survivors, as measured using the Functional Assessment of Chronic Illness Therapy-Fatigue (FACT-F) questionnaire. We hypothesize that FACT-F fatigue subscale scores will be lower for those in the time-restricted eating group compared to the control group at week 12, controlling for baseline levels.

Mechanistic (exploratory) aims: To assess the effects of a 12-week time-restricted eating intervention vs. an unrestricted eating pattern on circadian rhythm (mesor, amplitude, and acrophase from actigraphy), sleep parameters (e.g., sleep efficiency), and biomarkers of metabolism (fasting blood glucose, glucose excursions).

1. To assess cross-sectional associations between circadian rhythms, metabolism, and fatigue at baseline.
2. To explore associations between changes in circadian rhythms, metabolism, and fatigue from baseline to 6 weeks and baseline to 12 weeks.
3. To explore associations between adherence to the intervention and changes in the same measures.

2 \* Discuss the research design including but not limited to such issues as: probability of group assignment, potential for subject to be randomized to placebo group, use of control subjects, etc.:

This is a pilot randomized controlled trial. Participants will be randomized 1:1, intervention: control. Therefore, there is a 50% chance of any given participant to be in the control group, and a 50% chance of any given participant to be in the intervention group.

3 \* Describe the relevant prior experience and gaps in current knowledge. Describe any relevant preliminary data:

Cancer-related fatigue is a prevalent symptom of cancer and side effect of treatment that can be severe and persistent for years into survivorship. The etiology and pathophysiology of cancer-related fatigue are not well understood [1], though metabolic and circadian processes have been suggested to contribute to its severity. Cancer and cancer treatment, specifically chemotherapy [2-4], disrupts circadian rhythm. Environmental signals that regulate circadian rhythm, or 'zeitgebers' include physical activity, light, and food intake. Several studies have used bright light therapy to entrain circadian processes and have shown positive effects on fatigue among cancer survivors [5, 6]. Also, there is emerging evidence that time-restricted eating can entrain circadian rhythm, but not yet in the cancer population [7]. However, there have been no studies, to our knowledge, that test the ability of time-restricted eating to address cancer-related fatigue.

We recently completed a single-arm feasibility trial in which we investigated whether cancer survivors with persistent fatigue were willing and able to eat within a 10-hour window every day for two weeks. In total, 36/39 (92%) completed all questionnaires and daily diaries. Our preliminary data show that 80% had an average eating window  $\leq 10$  h and the average eating window was 9 hours, 14 minutes. There were no severe adverse events or rapid weight loss (mean $\pm$ SD change in weight:  $-1.3\pm 2.5$  lbs). Patients reported meaningful improvements in fatigue for both the FACT-F fatigue subscale (mean change $\pm$ SD=  $5.3\pm 8.1$  points,  $p<0.001$ , effect size=0.55) and the FACT-F total score (change  $9.3\pm 13.3$ ,  $p<0.001$ , effect size=0.50). We concluded that cancer survivors were willing and able to adhere to a 10-h TRE intervention. The program was feasible and safe, and fatigue improved with moderate effect sizes after two weeks.

4 \* Provide the scientific or scholarly background, rationale, and significance of the research and how it will add to existing knowledge:

Cancer-related fatigue affects at least 30-90% of patients undergoing chemotherapy, depending on the type of cancer and treatment as well as the method used to diagnose cancer-related fatigue [8, 9]. It is not relieved by sleep or rest, and its severity can greatly hinder the ability to perform activities of daily living and decrease quality of life. The mechanisms behind the etiology and pathophysiology of cancer-related fatigue seem to be related in part to inflammation, hypothalamic-pituitary-adrenal (HPA) activation dysfunction, metabolic and/or endocrine dysregulation, or other mechanisms, but are largely not understood, thereby thwarting the development of effective preventative strategies and treatments [1].

Circadian rhythms are biological diurnal cycles that work in synchrony to regulate hormone secretion, the sleep/wake cycle, core body temperature, and other processes. Circadian rhythm and human health have a bidirectional relationship, and circadian disruption is associated with a broad range of pathologies including, purportedly, cancer-related fatigue [2, 10, 11]. Circadian regulation occurs via genetic and physiological processes, and is important to maintain homeostasis of the endocrine system, autonomic nervous system, and nutrient metabolism [12, 13]. The importance of maintaining circadian rhythm is clear when traveling across time zones, and 'jet lag' is a common experience of fatigue when the circadian clock is disrupted [13]. Chemotherapy treatment disrupts circadian rhythm, and changes in circadian rhythm are associated with fatigue [2].

Regulation of circadian rhythm relies heavily on regular sleep habits, and interventions to regulate circadian clock currently include light therapy, exercise, melatonin supplementation, and more recently, nutrient timing [13]. Indeed, there are consistent animal and human data demonstrating that aberrant feeding/eating patterns dysregulate objective circadian clock measures (i.e., expression of genes that show strong diurnal oscillations) [14]. In an observational study among 156 healthy American adults in California, Gill and Panda [15] showed that approximately 50% of people eat within a window greater than 14.75 hours per day; only 10% eat within a window 12 hours or less [12]. Similar results were observed in our pilot feasibility trial—out of 60 people expressing interest in the trial, only 5 (8%) already ate within a 10-h window. A consistent, shorter window of eating, for example 10 hours or shorter, may aid in the regulation of the circadian clock and improve metabolic homeostasis with broad health outcomes [12, 16, 17]. Restricting eating to a certain time window is called 'time-restricted eating' (TRE).

TRE as a therapeutic approach has garnered a large appreciation in the literature and in the public in the last decade for its ability to mediate the circadian clock and prevent and treat various pathologies [7, 16, 17]. TRE involves restricting the consumption of calories to a short window (4-12 hours) during normal waking hours, for example 8am-6pm; water is never restricted. Human (time-restricted eating) and rodent (time-restricted feeding) studies have shown that TRE helps to maintain metabolic homeostasis and, as a result, prevents excess body weight, improves sleep, and attenuates age- and diet-induced heart disease (review [17]). One study clearly demonstrated the effects of nutrient timing on metabolic regulation: time-restricted feeding vs. time-unrestricted feeding of mice led to weight loss despite equal energy intake [18]. In humans, Gabel et al. performed an 8-h TRE study among obese adults for 12 weeks (n=23) [19]. Despite the diet being ad libitum, caloric intake decreased  $341\pm 53$  kcal/day. Body weight decreased  $2.6\pm 0.5$ %, and systolic blood pressure decreased  $7\pm 2$  mmHg. However, there were no significant changes in body composition, circulated lipids, fasting blood glucose, or fasting insulin. Also, Wilkinson et al. performed a 10-h time restricted eating study among patients with metabolic syndrome for 12 weeks (n=19) [12]. They observed improvements in sleep efficiency and quality, a safe rate of decrease in body weight and body fat percentage, a reduction in total and low density lipoprotein (LDL) cholesterol, and reductions in systolic and diastolic blood pressure [12]. While these studies were implemented for 12 weeks, benefits have been seen in glucose and lipid metabolism and circadian clock gene expression in as short as 4 days [20].

To date, aside from our own single-arm feasibility trial, TRE has only been studied in healthy participants or those who are overweight, obese, or with metabolic disorders (Lowe et al. [21] and references within the review by Wilkinson et al. [12], but not yet the cancer population [7]). These studies have collectively shown that a 10-h TRE window is feasible, safe, and effective at improving metabolic markers among their respective populations. Thus, the next logical step is to evaluate TRE vs. a control arm in a randomized controlled trial with the ultimate goal of evaluating its effectiveness to treat cancer-related fatigue.

This study will fill a large gap in the literature by being the first study, to our knowledge, to test the effects of time-restricted eating vs. a control arm on cancer-related fatigue.

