## Sample Size and Data Analysis

If you uploaded a separate research protocol document in the 'Research Protocol' page, cite the applicable section and page numbers from that document in the answer boxes below.

1 \* Provide the rationale and sample size calculations for the proposed target population:

This is a two-arm pilot randomized controlled trial that will assess the feasibility of recruitment and retention to a 12-week TRE trial facilitated by the myCircadianClock app as well as the preliminary efficacy of TRE vs. a control arm on the treatment of cancer-related fatigue.

It is common that single-arm pilot studies implementing dietary interventions recruit 10-40 participants (e.g., TRE study among overweight older adults, n=10; ketogenic diet among patients with recurrent glioblastoma, n=20; lifestyle intervention including diet among overweight breast cancer survivors, n=14). In total, 30 participants will be recruited, and approximately 10-20% attrition is anticipated, providing evaluable data from approximately 25 participants. We had more dropouts than anticipated and are upping our sample size to 50 participants so that we can have about 25 participants with evaluable data.

2 \* Provide the plan for data analysis. Include in the description the types of comparisons that are planned (e.g., comparison of means, comparison of proportions, regressions, analysis of variance, etc.), which is the primary comparison/analysis, and how the analyses proposed will relate to the primary purposes of the study:

We will conduct an interim analysis of feasibility after 10 participants have been enrolled. If any unanticipated barriers arise in regard to feasibility of recruitment, data collection, and/or retention, logistical changes will be made to the protocol as appropriate.

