Aim 1 assesses the feasibility of time-restricted eating over 12 weeks. We will note how many people we can screen; how many we can approach; how many are eligible; how many consent; and what percentage provide evaluable data at baseline and 12 weeks. Using data from myCircadianClock, we will extract how many days the participants ate within a 10-h window and the average length of the eating window at baseline, week 6, and week 12. We will consider a participant "adherent" if they ate within the 10-h window at least 80% of days. This goal is based on prior TRE studies. In regard to retention, it is hypothesized that at least 80% (24 out of 30) of those who provide baseline data also provide data at 12 weeks; this goal is based on colleagues' prior behavioral intervention studies with supportive care outcomes.

Aim 2 aims to provide estimates of efficacy comparing time-restricted eating vs. control on fatigue. Linear mixed models (LMMs) for longitudinal data will be used to assess the intervention effect on continuous outcomes (e.g., fatigue) accounting for correlations between the repeated measures. Generalized Linear Mixed Model (GLMM) analyses will be conducted to assess the effect of the intervention on count outcomes. The fixed effects included in the models will be treatment group (TRE versus control), time (baseline, 6 and 12 weeks), group-by-time interaction term and relevant covariates. Random effects will include individual patients. The hypotheses will be tested by evaluating the interaction term of group and time (i.e., 12 weeks). The results of the analyses together with the mean and SD of FACIT-F values as well as change scores will be used in planning future RCTs. All hypothesis testing will be at the two-sided level of 0.05. Following the intent-to-treat principle, all participants will be analyzed as randomized, regardless of their adherence with the intervention.

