**2 \* Describe procedures for orderly termination:**  
Upon completion of data collection and return of the actigraph, each participant will be thanked for their participation in the study and compensated for their time.

If a participant withdraws (or is withdrawn) before the end of the study, they will be paid for the time they spent providing data and the study team will not contact the person anymore. A 10-20% withdraw rate is built into the study design and recruitment goal, so there should not be a need to replace participants who withdraw before completing the study.

**3 \* Describe procedures that will be followed when subjects withdraw from the research, including partial withdrawal from procedures with continued data collection:**  
If a participant wishes to withdraw from the study, we will ask if the participant would like to continue participation in some but not all of the research activities. If they would like to participate in only some of the research activities, we will note which ones and the participant will not be formally withdrawn from the study. If they wish to withdraw completely, a written withdrawal request is required and should be sent to the PI (email preferred). The written request for withdrawal will be included in the participant's study record as documentation of the reason for removing a participant from the study. If a participant makes a verbal request and does not provide a written request, the verbal request will be documented by the study team member who receives the request and added to the participant's study record. Data that have been collected thus far will be analyzed.

ID: VIEW4E1B5251F800  
Name: v2\_Withdrawal of Participants

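### The Aim 1 adherence target counts only TRE participants with evaluable data, so at the loss now planned for it could be met while far fewer than 80% of those randomised to TRE are shown to be adherent.

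*Combined protocol and SAP*

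**What the plan says.** Under Justification, Objective, & Research Design (item 1), Aim 1 has two hypotheses. The first covers both arms: "We hypothesize that 80% of participants will provide evaluable data regarding their eating window via the app at baseline and 12 weeks". The second covers adherence: "at least 80% of participants who are in the time-restricted eating arm and provide evaluable data will eat within a daily average window" of 10 hours or less. Neither is made a condition of the other.

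Sample Size and Data Analysis (item 1) keeps the planning statement for 30 recruits, "approximately 10-20% attrition is anticipated, providing evaluable data from approximately 25 participants". It then reports more dropouts than expected and says the team is "upping our sample size to 50 participants so that we can have about 25 participants with evaluable data".

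Item 2 of that section adds a retention hypothesis, "at least 80% (24 out of 30) of those who provide baseline data also provide data at 12 weeks". It also calls a participant adherent if at least 80% of days fell within the 10-hour window, with no denominator or success threshold for the proportion adherent. No section says how a TRE participant without evaluable data counts towards adherence.

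On timing, Participant Selection (item 2) treats a person as enrolled at signed consent, while Study Procedures (item 1) places randomisation after the baseline week. Allocation is equal: "Participants will be randomized 1:1, intervention: control".

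**The concern.** A success rule restricted to those who supply data can be satisfied by a minority of those assigned to the intervention when many supply none. At 10-20% attrition the choice of denominator matters little. At one half it can decide whether the 80% mark is reached.

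The missing people may also differ from the rest. Adherence is measured only by self-logging in the app, so someone who stops restricting and stops logging leaves the denominator and is not counted as a failure. The note on adherence in the analysis section itself expects some non-compliance in the TRE arm.

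Aim 1 concerns the feasibility of TRE over 12 weeks, and Study Procedures (item 4) says the data will inform a follow-on trial. An evaluable-only rate carried forward as the expected adherence of those assigned to TRE would make that trial's planning too optimistic.

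**Working it through.** **Inputs.** Adherence target 80% of evaluable TRE participants (Aim 1). 50 recruited and about 25 evaluable, and before that 30 recruited with 10-20% attrition (Sample Size and Data Analysis, item 1). Allocation 1:1. I assume that evaluable means the same in the sample-size section as in Aim 1.

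**Reproducing the plan's figures.**
- 30 x (1 - 0.10) = 27 and 30 x (1 - 0.20) = 24, consistent with the stated 25 or so.
- 24/30 = 80%, as stated for retention.
- Implied loss now: 1 - 25/50 = 50%. In reverse, 25 / (1 - 0.50) = 50, the stated recruitment figure.

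**Smallest adherent share of those randomised to TRE that still meets the target.** The formula is (1 - loss after randomisation) x 0.80.
- 10% loss: 0.90 x 0.80 = 72%
- 20% loss: 0.80 x 0.80 = 64%
- 50% loss: 0.50 x 0.80 = 40%

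**In whole participants, if all 50 are randomised and loss is later and equal by arm.** 25 are randomised to TRE and 12 or 13 are evaluable.
- 12 evaluable: 0.80 x 12 = 9.6, so 10 are needed; 10/25 = 40% (exact 95% CI 21-61%).
- 13 evaluable: 0.80 x 13 = 10.4, so 11 are needed; 11/25 = 44%.
- With all 25 as denominator, 80% would need 0.80 x 25 = 20 adherent participants.

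**If some loss precedes randomisation (splits assumed), with 12-13 evaluable in the TRE arm.**

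| Randomised to TRE | Loss after randomisation, both arms | Adherent share needed |
|---|---|---|
| 25 | 1 - 25/50 = 50% | 10/25 to 11/25 = 40-44% |
| 20 | 1 - 25/40 = 37.5% | 10/20 to 11/20 = 50-55% |
| 15 | 1 - 25/30 = 17% | 10/15 to 11/15 = 67-73% |

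**If loss differs by arm (assumed range, 25 randomised to TRE).** With 8 evaluable, 7 are needed: 7/25 = 28%. With 17 evaluable, 14 are needed: 14/25 = 56%.

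**Against the companion target.** If 80% of the TRE arm were evaluable, 20 of 25 would be, and 16 adherent would suffice: 16/25 = 64%. At 25 of 50 evaluable, the 80% evaluable-data target is missed by 30 percentage points.

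**The case against.** The strongest reply is that the adherence target does not stand alone. The evaluable-data and retention hypotheses are still in the plan, and at 50% loss after randomisation both would visibly fail. The analysis section also commits to reporting the percentage with evaluable data and to tabulating missing data and reasons by treatment group, and a CONSORT diagram is foreseen under Waiver/Alteration of Authorization. A careful reader could work out the all-randomised proportion. This stands, and it means the loss would not be hidden. It does not settle what the adherence figure means: the companion targets pool both arms, and adherence can be declared met whether or not they are.

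Four stronger readings are tempting and are not supported.
- That 40% is the plan's own figure. The plan gives 50 recruited and about 25 evaluable. It does not say that half are lost after randomisation, or from which arm.
- That the resizing abandons the 80% evaluable-data target. The planning figure contradicts it, but the hypothesis remains in the text.
- That those who abandon the window are the ones lost. This is plausible, but no section gives reasons for the dropouts. In the investigator's two-week study, 36 of 39 completed all questionnaires and diaries while 80% averaged 10 hours or less, so some people outside the window still supplied data. That study was much shorter.
- That the adherence target breaches the intent-to-treat statement. The sentence "all participants will be analyzed as randomized, regardless of their adherence with the intervention" belongs to the Aim 2 efficacy analysis and sets no denominator for Aim 1.

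It is also fair to object that a missing log is not proof of non-adherence. Payment requires three of four activities and partial withdrawal is allowed, so a participant can follow TRE without logging food. This limits what the all-randomised figure can claim.

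**Conclusion.** The concern holds in a conditional form. The adherence target excludes TRE participants without evaluable data, is not tied to the evaluable-data target, and now sits beside a planning assumption that about half of recruits will not be evaluable. If all 50 are randomised 1:1 and loss is later and equal by arm, 40-44% of those randomised to TRE would be enough to meet it. If part of the loss comes before randomisation the floor rises, to 50-55% with 20 randomised to TRE and to 67-73% with 15. The last range is close to the 64-72% implied by 10-20% attrition, so the size of the problem depends on the timing and arm of losses that the documents do not report.

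In every one of these cases the evaluable-only figure could reach 80% while the share of the TRE arm shown to be adherent is lower. That supports changing how adherence is reported. It does not support a claim that most people assigned to TRE would have failed to adhere.

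**What to change.** 1. For the Aim 1 adherence conclusion, report the proportion of all participants randomised to TRE who are shown to be adherent, counting those without an evaluable week 12 log as not shown adherent. Place the evaluable-only proportion beside it, both with exact 95% confidence intervals.
2. State that feasibility of 12-week TRE will not be concluded from the evaluable-only proportion alone.
3. Say which adherence definition applies: the average window in Aim 1, or the 80%-of-days rule in Sample Size and Data Analysis (item 2).
4. Reconcile with 50 recruits the figures that still reflect 30: about 15 per arm in Study Procedures (item 1), 24 of 30 in Sample Size and Data Analysis (item 2), and "A 10-20% withdraw rate is built into the study design and recruitment goal" in Withdrawal of Participants (item 2).

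The cost is some wording and one table row; no new data are needed. The reported adherence becomes less favourable, and the all-randomised proportion must be read as a lower bound because some participants may have followed TRE without logging.
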